8.5 Documentation of Adverse Events by Investigator

Subjects will be evaluated and questioned generally to identify AEs during the course of the study. Any events occurring prior to administration of the first dose, will be recorded on the Medical History eCRF. SAEs will be recorded on the Adverse Event eCRF from informed consent through 30 days following the last dose of CX-2009 and (for irAEs) through 90 days after administration of the last dose of CX-072. Events occurring after administration of the first dose of study drug will be recorded on the Adverse Event eCRF. AEs that occur up to and including 30 days after administration of the last dose of study drug must be reported in the EDC system.

All AEs spontaneously reported by the subject and/or in response to an open question from study personnel or revealed by observation, physical examination, or other diagnostic procedures will be recorded on the Adverse Event eCRF for that visit. Any clinically relevant deterioration in laboratory assessments or other clinical findings is considered an AE and must be recorded on the Adverse Event eCRF. In addition, an abnormal test finding will be classified as an AE if 1 or more of the following criteria are met:

- The test finding is accompanied by clinical symptoms;
- The test finding necessitates additional diagnostic evaluation(s) or medical/surgical intervention, including significant additional concomitant drug treatment or other therapy. Note: Simply repeating a test finding, in the absence of any of the other listed criteria does not constitute an AE;
- The test finding leads to a change in study drug dosing or discontinuation of subject participation in the clinical research study; and
- The test finding is considered clinically significant by the Investigator based on his/her medical judgment. If an abnormal laboratory result is recorded as an AE, then the corresponding laboratory value must be marked clinically significant in the database. Similarly, if an abnormal laboratory value is marked clinically significant in the database, there should be a corresponding AE entered.

Wherever possible, a specific disease or syndrome rather than individual associated signs and symptoms should be identified. However, if an observed or reported sign or symptom is not considered a component of a specific disease or syndrome by the Investigator, it should be recorded as a separate AE. Laboratory data are to be collected as stipulated in this Module. Clinical syndromes associated with laboratory abnormalities are to be recorded as appropriate (eg, diabetes mellitus rather than hyperglycemia).

8.6 Notification About Serious Adverse Events and Suspected Unexpected Serious Adverse Reactions

Suspected unexpected serious adverse reactions (SUSARs) for CX-2009 and CX-072 will be distributed to the relevant regulatory authorities, independent ethics committees (IECs), institutional review boards (IRBs), and sites participating in CX-2009 clinical studies. SUSARs for CX-072 will be distributed to the relevant regulatory authorities, ethics committees, IRBs, and sites participating in the CX-072 clinical studies.

8.6.1 Investigator Reporting to Sponsor

All SAEs that occur during the course of the study must be reported to the Sponsor and Medpace Clinical Safety within 24 hours of the knowledge of the occurrence (this refers to any AE that meets any of the aforementioned serious criteria). In addition, all SAEs that occur up to and including 30 days following the last dose of CX-2009 and (for irAEs) through 90 days after administration of the last dose of CX-072 must be reported to the Sponsor within 1 working day from when the Investigator becomes aware of the SAE.

To report the SAE, the Investigator must record the SAE on the AE eCRF in the EDC system as well as any relevant eCRF forms (eg, drug dispensation eCRF, applicable laboratory eCRF). When the AE eCRF is completed, Medpace Safety personnel will be notified electronically and will retrieve the form. If the event meets serious criteria and it is not possible to access the EDC system, send an e-mail to Medpace Safety at [contact] or call the Medpace SAE hotline (phone number listed below), and fax the completed paper SAE Form to Medpace (fax number listed below) within 24 hours of awareness (see Table 12 for contact information). When the EDC system becomes available, the SAE information must be entered within 24 hours of the system becoming available.

Table 12. Safety Contact Information: Medpace Clinical Safety

	Medpace SAE Reporting Line – USA	Medpace SAE Reporting Line – Europe
[contact], dial 3 or [contact], dial 3	[contact]
[contact] or [contact]	[contact]
e-mail	[contact]	[contact]

Investigators must report to the Sponsor any SAE, whether or not considered drug related, including those listed in the Module or IB. The report must include an assessment of causality.

For all SAEs, the Investigator is obligated to obtain and provide information to the Sponsor in accordance with the timeframes for reporting specified above. In addition, an Investigator may be requested by the Sponsor to obtain specific additional follow-up information in an expedited fashion. This information may be more detailed than that captured on the SAE Form. In general, this will include a description of the AE in sufficient detail to allow for a complete medical assessment of the case and independent determination of possible causality. Information on other possible causes of the event, such as concomitant medications and illnesses must be provided. In the case of a subject death, a summary of available autopsy findings must be submitted as soon as possible to the Sponsor or its designee.

8.6.2 Serious Adverse Events Follow-Up

The Investigator must continue to follow the subject until the SAE has subsided or until the condition becomes chronic in nature, stabilizes (in the case of persistent impairment), or the subject dies.

Within 24 hours of receipt of follow-up information, the Investigator must update the AE eCRF and any other relevant eCRFs for the study. If requested, the Investigator must submit any supporting documentation (eg, subject discharge summary or autopsy reports) to Medpace Clinical Safety via fax or e-mail. If it is not possible to access the EDC system, refer to the procedures outlined above for initial reporting of SAEs.

8.6.3 Reporting to Regulatory Agencies and Central Institutional Review Board/Independent Ethics Committees

The Sponsor will report all relevant information about SUSARs that are fatal or life threatening as soon as possible to the FDA as applicable, applicable competent authorities in all the Member States concerned, and the Central IRB/IEC and in any case no later than 7 days after initial knowledge by the Sponsor of such a case. After the initial 7-day SUSAR report, a final 15-day SUSAR report will be submitted (ie, 8 days after the initial 7-day notification). Subsequently, follow-up for fatal or life-threatening SUSARs will be communications within 15 days.

All other SUSARs will be reported to the FDA as applicable, applicable competent authorities, and the Central IRB/IEC as soon as possible but within a maximum of 15 days of first knowledge by the Sponsor.

The Sponsor will inform all Investigators as required with instructions to submit to local IRBs/IECs per local requirements.

8.7 Rapid Notification of Adverse Events of Special Interest

In addition to SAEs, the following AEs will be reported to the Sponsor or its designee within 24 hours even if the nature of the AE is not deemed serious:

- AEs that potentially meet DLT criteria,
- \geq Grade 3 eye disorders (including blurred vision),
- \geq Grade 2 infusion reactions whether or not the event is a DLT,
- Any Grade 2 neurotoxicity,
- Any potential Hy's Law case (ie, ALT or AST $>3 \times$ ULN with concurrent total bilirubin $>2 \times$ ULN and ALP $<2 \times$ ULN, with lack of alternate etiology); and

For Parts D1, D2, E1, and E2: Any of the following irAEs defined as: AEs requiring the use of systemic corticosteroids within 30 days after the AE onset date with no clear alternate etiology, or requiring the use of systemic hormonal supplementation:

- Pneumonitis,
- Colitis,
- Hepatitis (including AST or ALT elevations $>3 \times$ ULN or bilirubin $>1.5 \times$ ULN),
- Nephritis (including serum creatinine $>1.5 \times$ ULN),
- Pancreatitis,
- Motor and sensory neuropathy (including Guillain-Barré syndrome and myasthenia gravis),
- Myocarditis,
- Encephalitis or meningoencephalitis,
- Endocrinopathies (including but not limited to hypothyroidism, hyperthyroidism, hypophysitis, diabetes mellitus, and adrenal insufficiency),
- Autoimmune ocular toxicities (eg, uveitis),
- Skin reactions including Stevens-Johnson syndrome or toxic epidermal necrolysis, and
- Diarrhea.

Please refer to Section 8.6 and the Core ([Appendix A](#)) for reporting SAEs, DLTs, and events of special interest.

8.8 Module-Specified Events

Subjects with advanced cancer enrolling in this study who have received prior treatment may have some degree of bone marrow suppression from prior therapy and/or laboratory abnormalities due to underlying disease status. Only changes in the grade of baseline laboratory values that require intervention (eg, transfusions, delay in study drug administration) should be reported as AEs.

Common AEs observed with other maytansinoid or MTI (eg, auristatin) ADCs may be expected for CX-2009. These include:

- Blood and lymphatic system disorders: neutropenia, thrombocytopenia, and lymphopenia;
- Nervous system disorders: peripheral neuropathy (sensory and motor) and paresthesia;
- Eye disorders: blurred vision, dry eyes, and keratopathy (including corneal cyst, corneal disorder, corneal epithelial microcysts, keratitis, limbal stem cell deficiency, and punctate keratitis);
- General disorders and administration site conditions: fatigue, pyrexia, pain, confusion, and headache;
- Hepatotoxicity (including increases in AST or ALT);
- Hypokalemia;
- Hypomagnesemia;
- Pulmonary disorders: interstitial lung disease;
- Infections and infestations: upper respiratory tract infection;
- Gastrointestinal disorders: nausea, diarrhea, abdominal pain, vomiting, decreased appetite, and constipation;
- Skin and subcutaneous tissue disorders: rash and pruritus; and
- Respiratory, thoracic, and mediastinal disorders: cough and dyspnea.

Common AEs (>15%) observed with the use of CX-072 (10 mg/kg administered every 21 days; n=114) include:

- Fatigue (34%)
- Anemia (25%)
- Decreased appetite (23%)
- Diarrhea (22%)
- Nausea (22%)
- Increased AST (19%)
- Vomiting (18%)
- Cough (16%)
- Dyspnea (16%)

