1.3.4.1 Summary of CX-2009 Clinical Safety

A total of 92 subjects treated with CX-2009 had available safety data. All but 6 subjects received CX-2009 once every 21 days at doses ranging from 0.25 mg/kg to 10 mg/kg. Six subjects received CX-2009 once every 14 days at a dose of 6 mg/kg. Please refer to the Investigator's Brochure (IB) for the most up-to-date information.

Overview of Treatment-emergent Adverse Events

Approximately 91.3% (84 of 92) of subjects had adverse events (AEs) that were judged by the Investigator to be related to study treatment. Forty-two (45.7%) had ocular toxicity that was related to CX-2009, with symptoms similar to other DM4 ADCs.

Twenty-six (28.3%) subjects experienced peripheral neuropathy related to CX-2009. The majority (13/26) had events that were Grade 1. Five subjects had Grade 3 peripheral neuropathy related to CX-2009.

Twenty (21.7%) subjects experienced infusion-related reactions (IRRs), the majority of which were Grade 1 or 2 (1 subject had a Grade 3 IRR). A previous analysis noted that the majority of subjects who had an IRR at the first infusion cycle, did not experience recurrence at subsequent infusions when premedication was administered.

Treatment-related SAEs and Treatment-related AEs Grade 3 or Higher

Eleven (12.0%) subjects experienced treatment-related serious adverse events (SAEs). Thirty-four (37.0%) subjects experienced Grade 3/4 treatment-related adverse events (TRAEs), including 10 with ocular toxicity (n = 8 Grade 3, n = 2 Grade 4) and 5 with peripheral neuropathy (all Grade 3).

There was 1 death related to study treatment according to Investigator's assessment.

Refer to the most recent version of the CX-2009 IB for the most updated and complete safety data.

Dose-Limiting Toxicities

One DLT was observed in Part A (8 mg/kg every 21 days); a Grade 3 event of vomiting that resolved (22 subjects were treated at this dose and schedule). No DLTs were observed at 9 and 10 mg/kg in 9 and 8 subjects, respectively.

Three DLTs were reported in 2 out of 5 evaluable subjects who received CX-2009 at a dose of 6 mg/kg every 14 days (Part C1) including a Grade 3 increased aspartate aminotransferase (AST) and a Grade 3 increased alanine aminotransferase (ALT) in 1 subject, and a Grade 3 peripheral neuropathy in another subject.

Treatment-emergent Adverse Events Related to CX-2009 at the Every 21-day Monotherapy RP2D of 7 mg/kg

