3.3 Dose-Limiting Toxicity

All AEs will be captured according to the National Cancer Institute Common Terminology Criteria for Adverse Events (NCI CTCAE) v4.03 (and considered for assessment of DLTs as outlined by the criteria in [Table 5](#)).

Table 5. Dose-Limiting Toxicity

Suspected DLT Criteria	DLT	
	Yes	No
Grade 5 AEs judged by the Investigator to be treatment-related or judged by the Sponsor as treatment-related, regardless of Investigator attribution.	X	
Grade 4 AEs* judged by the Investigator to be treatment-related or judged by the Sponsor as a DLT, regardless of Investigator attribution.	X	

*Grade 4 Exceptions
 
 • The following Grade 4 hematologic AEs: 
 – Grade 4 lymphopenia; and – Grade 4 neutropenia lasting <7 days that is not associated with fever, or other clinically significant symptoms, or is corrected with supportive measures (eg, growth factors)/appropriate management. • Grade 4 electrolyte imbalances/abnormalities that are not associated with clinical sequelae and are corrected with supplementation/appropriate management within 72 hours of their onset. 		X

Grade 3 AEs** judged by the Investigator to be treatment-related or by the Sponsor, regardless of Investigator attribution, including:
 
 • Any Grade 3 AE that does not resolve to Grade ≤1 or to baseline with appropriate therapies within 7 days of onset; • Any Grade 3 febrile neutropenia; • Any clinically significant Grade 3 CNS event; • Any Grade 3 neurotoxicity; and • Any Grade 3 ocular toxicity (limiting self-care ADL) that does not resolve within 7 days and which did occur despite proper application of preventive measures. 	X	

**Grade 3 Exceptions
 
 • Isolated Grade 3 electrolyte imbalances/abnormalities that are not associated with clinical sequelae and are corrected with supplementation/appropriate management within 72 hours of their onset; • Grade 3 asthenia which persists for up to 7 days; • “Tumor flare” – defined as local pain, irritation, or rash localized at sites of known or suspected tumor; and • Grade 3 infusion reaction which resolves to ≤Grade 1 within 6 hours. 		X
Grade 2 pneumonitis, Guillain-Barré syndrome, transverse myelitis, myocarditis, pericarditis, and arrhythmias necessitating discontinuation of CX-072.	X	

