5.5.4.1 Dose Management for CX-2009

Dose delay or permanent discontinuation of CX-2009 may be required as dictated in [Table 8](#) and [Table 9](#).

Note: Where CX-2009 and CX-072 are administered in combination (Parts D1, D2, E1, and E2), if, in the opinion of the Investigator, a toxicity is considered to be due solely to one component of the study treatment (ie, CX-2009 or CX-072) and the dose of that component is delayed, modified, or permanently discontinued in accordance with the guidelines in the Module, the other component may be administered if there is no contraindication.

Table 8. CX-2009 Dose Modifications for Select Adverse Events

Adverse Event	Grade 1	Grade 2	Grade 3	Grade 4
Anemia	No action	No action	Hold until recovery to ≤Grade 2 with transfusion; re-challenge at same dose. ^a	Hold until recovery to ≤Grade 2 with transfusion; re-challenge at same dose ^a if Grade 4 recurs, permanently discontinue CX-2009.
Neutropenia	No action	No action	Hold until recovery to ≤Grade 2; re-challenge at same dose. ^a	Hold and consider supportive measures until recovery to ≤Grade 2; re-challenge at same dose. ^a
Thrombocytopenia	No action	No action	PLT 25,000/mm ³ – <50,000 mm ³ Hold until platelet count recovers to ≤Grade 1 and then treat at same dose level.	PLT <25,000/mm ³ Hold until platelet count recovers to ≤Grade 1 and then treat at same dose level.
Increased serum transaminases (AST/ALT) Note: Corticosteroids may be considered for the management of liver enzyme elevations	No action	No action	Hold until AST/ALT recovers to ≤Grade 2 and then treat at same dose level.	Permanently discontinue CX-2009.
Hyperbilirubinemia	No action	Hold until total bilirubin recovers to ≤Grade 1 and then treat at same dose level.	Hold until total bilirubin recovers to ≤Grade 1 and then treat at same dose level.	Permanently discontinue CX-2009.

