Peripheral neuropathy (sensory motor)	No action	For new or worsening Grade 2 neuropathy, hold CX-2009 until neuropathy improves to Grade 1 or baseline.	For new or worsening Grade 3 neuropathy, hold CX-2009 until neuropathy improves to Grade 1 or baseline. Restart at same dose level. ^a Please note that a dose reduction may be considered in consultation with the Medical Monitor. Discontinue treatment permanently if no improvement within 2 weeks.	For new or worsening Grade 4 neuropathy, hold CX-2009 until neuropathy improves to Grade 1 or baseline. Please note that a dose reduction may be considered; consultation with the Medical Monitor is required. Discontinue treatment permanently if no improvement within 2 weeks.
Life-threatening or Grade 4 reaction	NA	NA	NA	Permanently discontinue CX-2009.

^a Please note that dose reduction may be considered following consultation with the Medical Monitor.

ALT = alanine aminotransferase; AST = aspartate aminotransferase; NA = not applicable; PLT = platelet count.

Neutropenia. Neutropenia should be managed by dosing delays. The dose of CX-2009 should be held for Grade 3 or Grade 4 neutropenia until resolution to baseline or ≤Grade 2. Growth factor support should be considered for subsequent cycles in subjects who experience Grade 3 or Grade 4 neutropenia. In subjects with recurrent Grade 4 neutropenia despite the use of growth factors, discontinuation of CX-2009 should be considered.

The dose of CX-2009 should be held for Grade 3 AEs judged by the Investigator to be treatment-related that are not listed in Table 8 until resolution to baseline or Grade 0.

In the event of a major surgery (any intervention requiring more than local anesthesia), stop dosing; resume dosing after consultation with the Medical Monitor.

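### Sections 8.5 and 8.8 disagree on when a laboratory change is an adverse event, so a laboratory value that meets Table 5 can go uncounted as a DLT

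*Protocol*

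**What the plan says.** The Protocol gives two recording rules for laboratory findings.

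- Section 8.5 is broad: "Any clinically relevant deterioration in laboratory assessments or other clinical findings is considered an AE and must be recorded on the Adverse Event eCRF". It lists several criteria, any one of which is enough to make an abnormal test an AE. One is the investigator's judgement that the finding is clinically significant, with no need for treatment or a dosing change.
- Section 8.8 is narrow: "Only changes in the grade of baseline laboratory values that require intervention (eg, transfusions, delay in study drug administration) should be reported as AEs". The sentence before it concerns subjects who enter with marrow suppression or laboratory abnormalities from prior therapy or disease. The rule makes no exception for values that would qualify as DLTs.

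Neither section refers to the other, and no text ranks them.

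DLTs are assessed from recorded AEs. Section 3.3 says AEs are graded by CTCAE "and considered for assessment of DLTs as outlined by the criteria in" Table 5. The 24-hour notice in Section 8.7 covers "AEs that potentially meet DLT criteria". SAP Section 12.1 carries the DLT flag as a field of the AE listings and counts DLTs in the AE summary table.

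Table 5 makes a treatment-related Grade 3 event a DLT by its duration: "Any Grade 3 AE that does not resolve to Grade ≤1 or to baseline with appropriate therapies within 7 days of onset". The dosing rule in Section 5.5.4.1 uses a different threshold: "The dose of CX-2009 should be held for Grade 3 or Grade 4 neutropenia until resolution to baseline or ≤Grade 2".

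**The concern.** Whether a laboratory change is an AE depends on which section a site follows, and whether it can be a DLT depends on whether it is an AE. Table 5 asks about grade and duration, while 8.8 asks about intervention. An event can pass the first test and fail the second. Every such event is lost in the same direction, towards fewer laboratory DLTs.

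The DLT count is part of the primary objective of Parts A and C1. It drives the 3+3 rule, the mTPI-2 table and the suspension rule for the expansion parts. Cohorts are small, so a single event can matter.

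**Working it through.** **1. Can the gap be reached under the Protocol's own schedule?** Hematology is weekly (Appendix B, Tables 13 to 16). Take treatment-related Grade 3 neutropenia at the Day 8 visit that is Grade 2 on Day 15 and at the next infusion. Assume a baseline of Grade 1 or better and nominal visit days.

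| Rule | Result |
|---|---|
| Table 5 | Seven days after detection it is still Grade 2, so not back to Grade 1 or baseline; neutropenia is not among the Grade 3 exceptions. Meets the DLT criterion. |
| Section 5.5.4.1, Table 8 | Grade 2 on the infusion day calls for no hold. No delay. |
| Section 8.8 | No transfusion, no delay. Not reported as an AE, so never assessed as a DLT. |
| Section 8.5 | An AE if clinically relevant or judged clinically significant, and then a potential DLT. |

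Section 5.5.4.1 also asks sites to consider growth factor in later cycles after Grade 3 neutropenia. If it is given, the event becomes an intervention under 8.8. The gap concerns subjects who do not receive it.

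**2. Reproducing Figure 6.** The table was recomputed with a Beta(1,1) prior, target 0.30, both epsilons 0.05, subintervals of width 0.10, and DU when P(p > 0.30) exceeds 0.95. The prior and the 0.95 cut-off are conventional assumptions that the documents do not state. In rows 0 to 6, 82 of 83 cells match. The exception is 2/2 (D printed, DU computed), which is below the minimum of 3 evaluable subjects.

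**3. Losing one DLT at the permitted cohort sizes of 3 to 6 (printed Figure 6).**

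| n | Changes | No change |
|---|---|---|
| 3 | 1/3 S to E; 2/3 D to S; 3/3 DU to D | none |
| 4 | 1/4 S to E; 2/4 D to S; 3/4 DU to D | 4/4 |
| 5 | 2/5 D to E; 4/5 DU to D | 1/5, 3/5, 5/5 |
| 6 | 2/6 S to E; 3/6 D to S; 4/6 DU to D | 1/6, 5/6, 6/6 |

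There are 3 + 4 + 5 + 6 = 18 starting counts with at least one DLT. Of these, 3 + 3 + 2 + 3 = 11 change. Ten move one step, and one (2/5) moves from D straight to E.

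**4. The 2/5 cell.** With a Beta(1,1) prior, P(p > 0.30 | x of n) = P(Bin(n+1, 0.30) ≤ x). For n = 5 the terms are 0.7⁶ = 0.118, 6(0.3)(0.7⁵) = 0.303 and 15(0.3²)(0.7⁴) = 0.324.
- x = 2: 0.118 + 0.303 + 0.324 = 0.744 after rounding from full precision (D).
- x = 1: 0.118 + 0.303 = 0.420 on the same basis (E).

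**5. Chance of an E decision at n = 5 if a share q of subjects with a DLT is lost.** E requires 0 or 1 recorded DLT, so with r = p(1 − q) the chance is (1 − r)⁵ + 5r(1 − r)⁴. The documents give no value for q; the range is assumed.

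| True DLT rate p | q = 0 | 10% | 25% | 50% |
|---|---|---|---|---|
| 0.30 | 52.8% | 59.1% | 68.5% | 83.5% |
| 0.40 | 33.7% | 40.9% | 52.8% | 73.7% |
| 0.50 | 18.8% | 25.6% | 38.1% | 63.3% |

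**6. Other rules.** In Table 6, 2/6 is above the MTD and 1/6 completes the dose. For the expansions, suspension needs a DLT rate above 30% in the first 6 subjects: 2/6 = 33% suspends and 1/6 = 17% continues.

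**The case against.** The best reply is that 8.8, read after its preceding sentence, covers only abnormalities present at entry, and that it says should where 8.5 says must. That reading is reasonable but does not close the gap. The rule concerns changes in grade, so a subject who enters with mild marrow suppression and worsens to Grade 3 still falls under it.

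Other objections limit the point and stand.

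- A reader might infer that a transient Grade 3 ALT shows the problem equally well. It does not on the scheduled visits. Chemistry between infusions (Days 8 and 15 on the 21-day schedule, Days 8 and 22 on the 14-day schedule) is electrolytes only. A Grade 3 ALT found at an infusion visit triggers a hold ("Hold until AST/ALT recovers to ≤Grade 2 and then treat at same dose level"), which 8.8 itself treats as reportable. That example needs an unscheduled draw.
- A reader might infer that the Part C1 decision was, or could have been, reversed. Section 1.3.4.1 records that "Three DLTs were reported in 2 out of 5 evaluable subjects who received CX-2009 at a dose of 6 mg/kg every 14 days", and one of the two subjects had only AST and ALT events. Those events were counted, the dose was judged not tolerated, and nothing shows that 8.8 would have excluded them.
- Figure 6 is not the only guide. Figure 7 tabulates events that interrupt or stop treatment, which 8.8 does not hide. If the AST/ALT subject were removed and the remaining neuropathy subject's hold counted as an interruption, Figure 7 at 1/5 reads S, not E. The Sponsor and SRC are guided by these tables, not bound by them.
- The value does not disappear. SAP Section 12.4 grades laboratory results independently of AE entry and lists all results for subjects with any abnormal one. These outputs do not feed the DLT count, however.

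**Conclusion.** The conflict is real and unranked, and it can remove a qualifying laboratory DLT from the count, most plausibly through weekly hematology. The bias runs one way. One lost DLT changes 11 of 18 Figure 6 decisions at cohort sizes of 3 to 6, almost always by one step, and it decides the 3+3 and expansion rules at 2/6.

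The documents do not support the stronger claim that laboratory DLTs were lost, that any dose was wrongly selected, or that a lost event generally turns de-escalation into escalation. They give no frequency for such events, so the size of the bias is unknown. Step 5 shows only how the decision would respond to assumed losses.

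Enrollment stopped on 07 July 2020 with 99 subjects treated (SAP Sections 1, 4.2 and 8). What remains at stake is the accuracy of the final AE and DLT tables, and any reuse of the Module text.

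**What to change.** Reconcile 8.8 with 8.5 in one sentence, for example: *Section 8.5 governs the recording of laboratory findings; any laboratory value that would meet a Table 5 criterion is recorded as an AE and assessed as a potential DLT, whether or not intervention was required.* The second clause is needed because 8.5 alone still depends on a judgement of clinical relevance. There is no need to make every Grade 3 or higher laboratory change an AE; that would override the test in 8.5.

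Before database lock, query Grade 3 or higher laboratory values in the DLT window (21 or 28 days) that have no matching AE, and report how many were found and how each was resolved.

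The cost is one sentence and a query on data already held. Laboratory AE and DLT rates may become slightly less favourable. No treatment or dosing rule changes.
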